## **10: Recruitment:**

A total of 300 subjects will be enrolled, targeting 72 completers (36 males and 36 females) under the new study design. To date (April 2016), 45 subjects have signed consents with 23 completers under the previously approved protocol design. These subjects will not be asked to return for participation in the new study design.

## **11. Research Plan:**

### **A. Overview**

This will be a double-blind, placebo-controlled study, with 72 LITS (36 male and 36 female smokers) participating in five experimental sessions. All sessions will be conducted following overnight abstinence to control for recent nicotine intake. The lab sessions will be at least 24 hours apart to minimize carryover nicotine effect between sessions. In each experimental session, subjects will be randomly assigned to one of the five doses of nicotine (0.0125, 0.025, 0.05, 0.1 and 0.2 mg/70 kg or about 0.18, 0.36, 0.7, 1.4 and 2.8  $\mu$ g/kg). At the beginning of each experimental session, subjects will first sample the assigned nicotine dose and placebo (saline) condition that are randomly labeled as A or B. Beginning 15 minutes after the second sample dose, subjects will have the opportunity to choose between drug A or B every 15 minutes, for a total of ten opportunities over a 165-minute period. Immediately after subjects make their choice, drugs will be administered over 30 seconds using an infusion pump. The main outcome measure will be the number of nicotine self-administrations for each nicotine dose. The parameters of this nicotine self-administration procedure were based on our previous study (Sofuoglu et al. 2008a).

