#### **D. Drugs**

Nicotine: Nicotine bitartrate will be obtained from Interchem Corporation, Paramus, NJ. Nicotine solution for injection will be prepared by U.S. Specialty Formulations, Bethlehem, P.A.. Nicotine increases heart rate, peripheral vascular resistance, myocardial contractility, cardiac output, and blood pressure. Nicotine may cause nausea, vomiting, and diarrhea. Acute toxicity of nicotine occurs with high doses; 40-60 mg orally is considered lethal. Signs and symptoms of acute toxicity include nausea, vomiting, abdominal pain, hypersalivation, diarrhea, dizziness, confusion, hearing and vision problems, syncope, seizures, hypotension, irregular pulse, and death (Benowitz and Gourlay 1997; Kobayashi et al. 1999).

**Nicotine administration:** In our proposed study, nicotine will be administered over 30 seconds, via an IV catheter located in a forearm vein, using an infusion pump. We have followed these procedures in our previous studies (Sofuoglu et al. 2003, 2005, 2006b; 2008a, 2009a, b,c; Sofuoglu and Mooney 2009), which were completed without any adverse effects or safety concerns. For each experimental sessions, two IV infusions will be prepared in randomized, double-blinded fashion. The two infusions will be marked as either "A" or "B" on identical-looking IV labels. Depending on the randomization, one of the infusion will contain an active nicotine dose (0.0125, 0.025, 0.05, 0.1 and 0.2 mg/70 kg) and the other will contain saline. The total amount of nicotine solution in the active infusion will contain enough for 1 sample dose of 5 mL, 10 optional doses of 5mL each, and additional volume to prime the infusion line. The matching placebo infusion will also contain enough for 1 sample dose of 5mL, 10 optional doses of 5mL each, and additional volume to prime the infusion line.

The matching placebo infusion bags will also contain enough for 1 sample dose and 10 optional doses and for the line flush of 0.9% NaCl. The infusion bags will be labeled and dispensed to the study staff by the research pharmacy. [name] holds an IND for IV nicotine administration.

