75 Min	26	HR/BP, DEQ IV sampling Option 4
76 Min	27	HR/BP DEQ
77 Min	28	HR/BP,
78 Min	29	HR/BP, DEQ
80 Min	30	HR/BP, DEQ
90 Min	31	HR/BP, DEQ IV sampling Option 5

91 Min	32	HR/BP DEQ
92 Min	33	HR/BP,
93 Min	34	HR/BP, DEQ
95 Min	35	HR/BP, DEQ
105 Min	36	HR/BP, DEQ IV sampling Option 6
106Min	37	HR/BP DEQ
107Min	38	HR/BP,
108 Min	39	HR/BP, DEQ
110 Min	40	HR/BP, DEQ
120 Min	41	HR/BP DEQ IV sampling Option 7
121 Min	42	HR/BP DEQ
122 Min	43	HR/BP,
123 Min	44	HR/BP, DEQ
125 Min	45	HR/BP, DEQ
135 Min	46	HR/BP DEQ IV sampling Option 8
136 Min	47	HR/BP DEQ
137 Min	48	HR/BP,
138 Min	49	HR/BP, DEQ
140 Min	50	HR/BP, DEQ
150 Min	51	HR/BP DEQ IV sampling Option 9
151 Min	52	HR/BP DEQ
152 Min	53	HR/BP,
153 Min	54	HR/BP, DEQ
155 Min	55	HR/BP, DEQ
165 Min	56	HR/BP DEQ IV sampling Option 10
166 Min	57	HR/BP DEQ
167 Min	58	HR/BP,
168 Min	59	HR/BP, DEQ
170 Min	60	HR/BP, DEQ
180-240 Min	61	HR/BP, DEQ, EKG, SCF M-NWSC, BQSU, PANAS, SNACK and Discharge

\*Same measure will be obtained following saline and each nicotine administration. For brevity, only the measures after saline are shown.

Abbreviations: CO: Alveolar carbon monoxide, HR/BP: Heart rate/Blood pressure; EKG: Electrocardiogram; SCF: Symptom Checklist form; M-NWSC: Minnesota Nicotine Withdrawal Symptom Checklist; BQSU: Brief Questionnaire of Smoking Urges; PANAS: Positive and Negative Affective Schedule; DEQ: Drug Effects Questionnaire.

Experimental sessions: The schedule of events during the experimental sessions is shown in Table 1. Before the session begins, subjects will have an IV catheter placed and the baseline measures will be taken. Subjects will begin NSA as described below.

Nicotine self-administration procedure:

Apparatus: Saline and nicotine will be administered with two separate infusion pumps, which will be prepared with IV infusion bags randomly labeled as Drug A or B by the research pharmacist. Both the researchers and the subjects will be blind to the randomization. The infusion pumps will deliver saline and nicotine at a precise rate and volume.

Procedure: The NSA procedure will consist of two phases: Sampling and Nicotine Choice.

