Sampling: In each of the five test sessions, subjects will be randomly assigned to one of the five doses of nicotine: 0.0125, 0.025, 0.05, 0.1 and 0.2 mg/70 kg. Subjects will first receive saline and the assigned nicotine dose in a randomized order and double-blind fashion. Subjects will be informed that they will be receiving drug A or B, which may be nicotine or saline. This procedure will allow subjects to sample the nicotine and saline that will be available during that session. In addition, subjective and physiological responses to the sample nicotine dose and saline will be assessed.

Nicotine Choice procedure: Beginning 15 minutes after the sampling phase is completed, subjects will be asked to make a choice between drug A or B every 15 minutes for a total of ten choices over 150 minutes. The drug chosen by the subjects will be immediately delivered with the infusion pump over 30 sec in 5 ml of saline. This choice procedure has been used in our IV nicotine self-administration study as well as in many previous studies with various drugs of abuse (Sofuoglu et al. 1999, 2000, 2001; 2009c). One particular advantage of this model, compared to the ad lib models used in previous IV nicotine self-administration studies (Harvey et al. 2004; Rose et al. 2003), is the ability to control amount of nicotine delivered without interfering with the self-administration behavior.

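### The labels A and B are reused with a fresh random meaning in all five sessions, so a letter preference may carry over, dilute nicotine choice toward 50%, and hide a weakly preferred dose

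*Combined protocol and SAP*

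**What the plan says.** The combined protocol and SAP describes the labelling in three places. Section 11.A (Overview) says that in each session "subjects will first sample the assigned nicotine dose and placebo (saline) condition that are randomly labeled as A or B". Section 11.D (Drugs) says "For each experimental sessions, two IV infusions will be prepared in randomized, double-blinded fashion", and then "The two infusions will be marked as either 'A' or 'B' on identical-looking IV labels". Section 11.E (Study Procedures, Apparatus) refers to "IV infusion bags randomly labeled as Drug A or B by the research pharmacist". No session-specific labels are described.

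Each subject attends five sessions: "In each of the five test sessions, subjects will be randomly assigned to one of the five doses of nicotine" (section 11.E, Sampling). On what subjects hear, the same paragraph says "Subjects will be informed that they will be receiving drug A or B, which may be nicotine or saline". On re-sampling it says "This procedure will allow subjects to sample the nicotine and saline that will be available during that session". The gap between visits has a pharmacological reason only: "The lab sessions will be at least 24 hours apart to minimize carryover nicotine effect between sessions" (section 11.A).

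Under section 12 (Data analysis methods), the outcome is the number of nicotine choices out of 10 per session. The threshold is the lowest dose whose nicotine share is significantly above 0.5. The logistic mixed model has dose as a fixed category and subject as a random effect, with gender added for Hypothesis 1B. It has no term for session, current letter or previous letter.

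**The concern.** The task asks the subject to find out which letter is worth choosing and then to choose by letter ten times. At the next visit the same letters appear with their contents redrawn. A subject who left one session favouring B may start the next with some pull toward B, and that pull is right about nicotine only half the time. The 24-hour gap clears nicotine but not memory.

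The direction of any such effect is known, because choices driven by an old letter average 50%. The threshold is a main outcome and is decided by a significance test against 0.5. The dose steps are two-fold (0.0125, 0.025, 0.05, 0.1, 0.2 mg/70 kg), so missing one weakly preferred dose can move the reported threshold up by a factor of two. A fixed A-versus-B term would not deal with this, since the favoured letter differs by subject and session.

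**Working it through.** **1. The plan's own figure.** Section 12 (Rationale for sample size) gives 80% power for 67% against 50% with 72 subjects, two-sided alpha 0.05. Treat each subject as one binary unit and use a continuity-corrected normal test:

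- null standard error = √(0.25/72) = 0.0589; times 1.96 = 0.1155
- alternative standard error = √(0.67 × 0.33/72) = 0.0554
- (0.17 − 1/144 − 0.1155)/0.0554 = 0.858, so power = 80.5%

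Without the correction, power is 83.7%. The stated figure is reproduced, but this calculation does not use the ten choices per session.

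**2. Direction.** Let p be the true nicotine share at a dose and L the share of choices driven by an earlier letter (assumed; the documents give no value). The letters are re-randomised, so those choices average 0.5:

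- observed share in an affected session = (1 − L)p + 0.5L, a shift of −L(p − 0.5)

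First sessions have no earlier letter. If one fifth of the observations at each dose come from first sessions, the average shift is −0.8L(p − 0.5):

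| True p | L = 0.1 | L = 0.2 | L = 0.4 |
|---|---|---|---|
| 0.60 | 0.592 | 0.584 | 0.568 |
| 0.67 | 0.656 | 0.643 | 0.616 |

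At p = 0.5 the shift is zero.

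**3. Power on the planned outcome.** Simulation with 72 subjects, ten choices each, beta-binomial variation between subjects, a t-test of subject proportions against 0.5, and first sessions unaffected. The intraclass correlation (ICC) of 0.3 is assumed:

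| True p | L = 0 | L = 0.1 | L = 0.2 | L = 0.4 |
|---|---|---|---|---|
| 0.60 | 79% | 77% | 72% | 49% |
| 0.67 | 99.8% | 99.3% | 99.2% | 91% |

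Repeat runs agree to within about one point. At p = 0.5 the two-sided rejection rate stayed between 4.8% and 5.6% across the settings tried.

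**4. Sensitivity to the assumed ICC.** Power at L = 0, 0.2 and 0.4:

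| ICC | True p = 0.60 | True p = 0.67 |
|---|---|---|
| 0.1 | 97%, 89%, 60% | 100%, 100%, 97% |
| 0.6 | 57%, 51%, 38% | 96%, 93%, 82% |

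**5. Pattern over dose.** Take illustrative true shares of 0.52, 0.55, 0.60, 0.67 and 0.70 from lowest to highest dose. In affected sessions:

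- L = 0.2 at every dose: shifts of 0.004, 0.010, 0.020, 0.034 and 0.040 toward 0.5
- L falling from 0.5 to 0.1 as dose rises: 0.010, 0.020, 0.030, 0.034 and 0.020

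In neither case is the shift largest at the lowest dose.

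**The case against.** The strongest reply is that carryover is a hypothesis. No data in the documents show it. In the preliminary study (26 smokers, 0.1 to 0.4 mg, six choices per session) nicotine was not chosen more than saline overall; if few sessions produce a clear preference, there is little letter learning to carry. Both infusions are sampled again at the start of every session, each choice is followed by its own infusion, and subjects are told that either letter may be nicotine or saline. The consent form is not in the public text, so silence there does not show that subjects are never told the letters change.

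Much of this stands. Carryover is a risk and cannot be asserted as fact, and re-sampling reduces it. But re-sampling helps least when the sample is barely detectable, and the trial deliberately includes doses lower than its group has tested before. Telling subjects that a letter's content is unknown is also weaker than telling them that it is redrawn at each visit.

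Three stronger readings are tempting and not supported:

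- **That the pull is largest at the lowest doses.** The shift is L(p − 0.5), which shrinks as preference approaches 50%. The proportional loss would be largest there only if letter-driven choice rose as the dose became harder to feel, and the documents give no evidence on that.
- **That it steepens the dose-response curve.** A constant L multiplies every departure from 0.5 by the same factor below 1, which flattens the curve. Steepening would need a dose-dependent L.
- **That power for a 67% preference collapses.** A one-sample t calculation at 0.34(1 − L) with n = 72 gives 81%, 73%, 62% and 40% at L = 0, 0.1, 0.2 and 0.4. It treats each subject as one binary result (0.17/0.5 = 0.34) and applies carryover to first sessions too. The plan's own 0.34 belongs to the Aim 2 subjective effects. With ten choices and unaffected first sessions, the loss at 67% is small except at high L and high ICC.

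**Conclusion.** The concern holds as a possible attenuation of unknown size. The reuse of A and B across five re-randomised sessions is plain in the text. No described instruction breaks the link between visits, and no planned model term addresses it. Any carryover moves nicotine choice toward the null and does not raise false positives. The practical harm is confined mainly to weak preferences: at a true 60%, power falls from about 79% to between 77% and 49% for assumed letter-driven shares of 0.1 to 0.4 (ICC 0.3), while at a true 67% it stays at about 91% or more under the same assumptions. The possible consequence is a weakly preferred dose missed and a threshold reported too high. The letter-driven share, the ICC and the one-fifth of unaffected observations are all assumptions. This is a cheap improvement; it does not show that the planned design fails.

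**What to change.** Use a different neutral pair of letters in each session (for example A/B, C/D, E/F, G/H, J/K), randomised to nicotine and saline as now. Add one scripted sentence at the start of each session: letters from earlier visits do not apply today. This removes the shared letters as a route for carryover without needing to know its size. Dose assignment, blinding and visit schedule stay as they are.

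The cost is minor pharmacy label work and one line of script. If adopted mid-study, procedure will differ between earlier and later subjects, which should be recorded. For subjects tested under the reused letters, add a sensitivity analysis with session number and the previous session's nicotine letter, coded as same as or different from the current one. This would show whether carryover is present and how large. It would not by itself undo the dilution, because the same/different term averages out over the randomisation and leaves the dose means attenuated. A first-session-only analysis avoids the problem but has about 72/5 ≈ 14 subjects per dose, so it can only be supportive. Prevention by labelling is the better route.

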## **B. Medical Monitoring and Safety**

Subjects will be given a thorough physical examination prior to entry in the study. For nicotine administration sessions, a physician will be present and subjects will be attached to a cardiac monitor as well as a blood pressure and heart rate monitoring device. An IV catheter will be in place throughout the session. Subjects will be administered nicotine only if the systolic blood pressure is <150 mmHg and heart rate is <100 beats/minute. Subjects will be terminated from the study if the blood pressure at any time is >170/110 mm Hg, the heart rate is >120 beats/min, or if they develop signs and symptoms compatible with nicotine toxicity. Subjects will remain in the laboratory for at least an hour after the last nicotine administration. These procedures have been developed as part of our IND for IV nicotine.

## **C. Outcome Measures**

### Behavioral

Nicotine Self-Administration: Nicotine self-administration behavior will be measured with the number of nicotine administrations during the session.

### Physiological

Heart rate and blood pressure: Heart rate and blood pressure readings will be taken at intake for screening, and during the lab sessions to monitor nicotine's effects.

### Biochemical

1) Alveolar carbon monoxide: The CO measurement taken before the sessions will help to verify compliance with smoking abstinence. CO readings  $\leq$  8ppm will be used to verify compliance with overnight smoking as recommended by the SRNT Subcommittee on Biochemical Verification (Benowitz et al. 2002).

2) Serum estradiol and progesterone analysis (females only): Serum estradiol and progesterone levels will be measured before each lab session for use as covariates in our analysis, since female sex hormones may contribute to sex differences in nicotine responses (Smith et al. 2006; Sofuoglu et al. 2001; Zubieta et al. 2002).

4) Plasma/urine cotinine, 3-hydroxycotinine (3-HC), and nicotine levels: Plasma/urine samples of cotinine will be taken at intake to quantify the level of nicotine intake of the subjects. 3-HC is the main metabolite of cotinine and the ratio of 3-HC/cotinine, also known as the nicotine metabolite ratio, reflecting the activity of cytochrome P450 (CYP2A6) and thus, the rate of nicotine clearance. Plasma nicotine levels will also be measured before each session to ensure overnight abstinence from smoking. Assays for nicotine, cotinine, and 3-HC levels will be performed in [name] laboratory. Briefly, nicotine, cotinine and 3-HC are measured using HPLC coupled to tandem mass spectrometry (LC/MS/MS) employing stable isotope labeled internal standards as previously described.

### Subjective

#### Intake Measures:

1) Structured Clinical Interview for DSM-5 (SCID) for Axis I disorders: SCID is a semi-structured interview based on DSM-5 (American Psychiatric Association, 2013) and will be performed to diagnose Axis I psychiatric disorders.

2) Fagerstrom Test of Nicotine Dependence (FTND): This self-report measure assesses the degree of nicotine dependence and has been used widely in smoking studies (Heatherton et al. 1991)

3) Center for Epidemiologic Studies Depression (CES-D) scale: The CES-D is a 20-item self-report measure of depressive symptoms (Radloff 1977). This scale will be used at intake to control for baseline differences in depressive symptoms.

#### Session Measures:

1) Minnesota Nicotine Withdrawal Symptom Checklist (M-NWSC): Smokers will be asked to rate several nicotine withdrawal symptoms from on a 100 mm scale, "not at all" to "extremely." The items are derived from the M-NWSC (Hughes and Hatsukami 1986) and have been used in previous human laboratory studies (Eissenberg et al. 1996). The items include cigarette craving, irritability/anger, anxiety/tension, difficulty concentrating, restlessness, increased appetite, depressed mood, and insomnia.

2) Positive and Negative Affect Schedule (PANAS): The PANAS is a 20-item scale that assesses both negative and positive affective states (Watson et al. 1988). This scale is sensitive to the affective symptoms of tobacco withdrawal and predicts relapse to smoking (Kenford et al. 2002).

3) Brief Questionnaire on Smoking Urges (BQSU): This 10-item scale has been found to be highly reliable and reflects levels of nicotine deprivation (Bell et al. 1999; Morgan et al. 1999). This scale will be used to monitor cigarette craving.

4) Drug Effects Questionnaire (DEQ): Smokers will rate 5 items that are related to nicotine effect on a 100 mm scale, "not at all" to "extremely." The items are feeling the "drug strength," feel "good" drug effects, feel "bad" drug effects, liking the drug effects, and "head rush." This instrument allows rapid detection of nicotine effects and is adapted from a VAS (Soria et al. 1996).

#### Genetics

Blood samples for DNA extraction will be collected to examine whether any of the genes modify the effects of nicotine. Candidate genes will be selected from a list of genes hypothesized to be involved in nicotine's effects. The current list of genes includes but is not limited to genes for nicotinic and muscarinic receptors. To protect confidentiality, each subject's blood sample will be encoded with a numeric designation and the name of the individual will be stored in a separate database. The samples will be transferred to the Genetic Laboratory at the VA medical Center for processing and storage.

#### **D. Drugs**

Nicotine: Nicotine bitartrate will be obtained from Interchem Corporation, Paramus, NJ. Nicotine solution for injection will be prepared by U.S. Specialty Formulations, Bethlehem, P.A.. Nicotine increases heart rate, peripheral vascular resistance, myocardial contractility, cardiac output, and blood pressure. Nicotine may cause nausea, vomiting, and diarrhea. Acute toxicity of nicotine occurs with high doses; 40-60 mg orally is considered lethal. Signs and symptoms of acute toxicity include nausea, vomiting, abdominal pain, hypersalivation, diarrhea, dizziness, confusion, hearing and vision problems, syncope, seizures, hypotension, irregular pulse, and death (Benowitz and Gourlay 1997; Kobayashi et al. 1999).

**Nicotine administration:** In our proposed study, nicotine will be administered over 30 seconds, via an IV catheter located in a forearm vein, using an infusion pump. We have followed these procedures in our previous studies (Sofuoglu et al. 2003, 2005, 2006b; 2008a, 2009a, b,c; Sofuoglu and Mooney 2009), which were completed without any adverse effects or safety concerns. For each experimental sessions, two IV infusions will be prepared in randomized, double-blinded fashion. The two infusions will be marked as either "A" or "B" on identical-looking IV labels. Depending on the randomization, one of the infusion will contain an active nicotine dose (0.0125, 0.025, 0.05, 0.1 and 0.2 mg/70 kg) and the other will contain saline. The total amount of nicotine solution in the active infusion will contain enough for 1 sample dose of 5 mL, 10 optional doses of 5mL each, and additional volume to prime the infusion line. The matching placebo infusion will also contain enough for 1 sample dose of 5mL, 10 optional doses of 5mL each, and additional volume to prime the infusion line.

The matching placebo infusion bags will also contain enough for 1 sample dose and 10 optional doses and for the line flush of 0.9% NaCl. The infusion bags will be labeled and dispensed to the study staff by the research pharmacy. [name] holds an IND for IV nicotine administration.

**Justification for the nicotine doses:** For this proposal, we chose five doses of nicotine that are in low dose range including 0.0125, 0.025, 0.05, 0.1 and 0.2 mg/70 kg. The highest dose, 0.2 mg, is equivalent to the amount of nicotine delivered from one or two puff of a cigarette, which ranges from 0.05 to 0.2 mg/puff or 0.5 to 2.4 mg/cigarette 1.0 - 2.4 mg, delivered via 10 to 13 puffs (33, 81, 82). In our previous study, 0.2 mg/70 kg dose of nicotine produce positive subjective drug effects and were self-administered by male dependent smokers (34). The lowest dose will be 0.0125 mg/70 kg, lower than the amount estimated to be the addictive threshold for nicotine by B&H, 0.17mg nicotine/cigarette or 0.014 mg nicotine/ puff. We also included 3 additional doses of nicotine 0.025, 0.05, 0.1 mg, in between the 0.2 and the 0.0125 mg dose to provide a more detailed assessment of dose-effect function. These five doses of nicotine and placebo should allow for a detailed examination of individual differences in NSA at a low dose range

